The exploratory biomarker analyses listed are planned but may not be conducted if deemed as obsolete during later stages of the study; other exploratory analyses may be added based on emerging new findings. Details regarding the processing and shipping of all pharmacodynamic samples will be outlined in the study specific laboratory manual.

Statistical Considerations:

The analysis of all the clinical activity, safety, pharmacokinetic and pharmacodynamic parameters will be performed by Medivir AB or its designee.

Demographics and Baseline Characteristics

Descriptive statistics will be provided to summarize demographics and baseline characteristics.

Dose Escalation phase:

Primary Endpoint: Safety

The safety and tolerability of pembrolizumab and birinapant will be based on results of DLT incidence, reported SAEs, AEs, vital sign measurements, physical examinations, clinical laboratory information, ECOG performance status, and concomitant medications. Exposure to study drug and reasons for discontinuation will be tabulated. These data will be summarized descriptively for the ITT population overall.

Adverse events will be coded using the current *Medical Dictionary for Regulated Activities* (MedDRA) classification system, and will be summarized by system organ class and preferred term.

Additional safety analyses may be determined in order to most clearly describe toxicity rates and to further define the safety profile of pembrolizumab and birinapant.

Secondary Endpoints: Efficacy

Efficacy, as defined by ORR, will be assessed through RECIST v 1.1 until response or progression. Overall survival will also be assessed.

Results will be summarized descriptively. For parameters measured over time, data and changes from baseline will be summarized for each time point. **Exploratory Endpoints: Efficacy, Pharmacodynamics and Pharmacokinetics**

Efficacy, as defined by the ORR, will be assessed through RECIST v 1.1 until response or progression and will be subsequently analyzed through iRECIST (iCR, or iPR or iSD or after iUPD iCR, iPR or iSD or iCPD). iBOR will also be assessed. Results will be summarized descriptively.

Pharmacodynamic results will be summarized descriptively.

Pharmacokinetics results will be summarized descriptively. Population PK modeling may also be applied.

Dose Expansion phase:

Primary Endpoints:

Cohorts in colorectal cancer, ovarian cancer and cervical cancer: Clinical Activity

The primary objective will be evaluated using Simon's two-stage design. The null hypothesis that the true ORR is (5%, 7% and 10% for colorectal cancer, ovarian cancer and cervical cancer, respectively) will be tested against a one-sided alternative. The design yields a type I error rate of 5% and power of 80% for each of the three indications individually. No correction for multiplicity will be done. In addition to tabulate the result of the statistical tests, results will be summarized descriptively.

Various solid tumors cohort: Safety

The safety and tolerability of pembrolizumab and birinapant will be based on results of reported SAEs, AEs, vital sign measurements, physical examinations, clinical laboratory information, ECOG performance status, and concomitant medications. Safety data will be summarized descriptively. Exposure to study drug and reasons for discontinuation will be tabulated.

Adverse events will be coded using the current *Medical Dictionary for Regulated Activities* (MedDRA) classification system, and will be summarized by system organ class and preferred term.

Additional safety analyses may be determined in order to most clearly describe toxicity rates and to further define the

safety profile of pembrolizumab and birinapant.

Secondary Endpoints:

Cohorts in colorectal cancer, ovarian cancer and cervical cancer: Safety

The safety and tolerability of pembrolizumab and birinapant will be based on results of reported SAEs, AEs, vital sign measurements, physical examinations, clinical laboratory information, ECOG performance status, and concomitant medications. Safety data will be summarized descriptively by cohort and also summarized descriptively over cohorts within each of the two phases of the protocol. Exposure to study drug and reasons for discontinuation will be tabulated.

Adverse events will be coded using the current *Medical Dictionary for Regulated Activities* (MedDRA) classification system, and will be summarized by system organ class and preferred term.

Additional safety analyses may be determined in order to most clearly describe toxicity rates and to further define the safety profile of pembrolizumab and birinapant.

All Cohorts: Clinical Activity

Efficacy, as defined by PFS, CBR, Time to response and Duration of response, will be assessed through RECIST v 1.1 and until response or progression. Overall survival will also be assessed.

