18. Patients must have histologically or cytologically confirmed head and neck squamous cell carcinoma that is locally advanced or metastatic with no available therapy options that are known to provide clinical benefit per institutional standard of care. Patients with tumors with mutations for which there are available therapies that are known to provide clinical benefit, as defined by national authority and/or ratified by national guidelines or equivalent, must have progressed following these therapies in order to be eligible for this study *(various solid tumors cohort: head and neck squamous cell carcinoma groups only)*.
19. Patients with head and neck squamous cell carcinoma who are to participate in the group of checkpoint inhibitor experienced patients must have received prior therapy with an anti-PD-1 or anti-PD-L1 antibody, administered either as monotherapy, or in combination with other therapies. Patients must have received at least two doses of an approved anti-PD-1/anti-PD-L1 antibody and have experienced documented radiographic progression of disease by RECIST v1.1. The initial evidence of disease progression is to be confirmed by a second assessment no less than four weeks from the date of the first documented disease progression in the absence of rapid clinical progression. The date for documentation of initial progression will be considered the date for disease progression. Progressive disease must have been documented during or within 12 weeks after last dose of such treatment. *(various solid tumors cohort head and neck squamous cell carcinoma, checkpoint inhibitor experienced group only)*.
20. Patients must have histologically or cytologically confirmed small cell lung carcinoma that is locally

advanced or metastatic with no available therapy options that are known to provide clinical benefit per institutional standard of care. Patients with tumors with mutations for which there are available therapies that are known to provide clinical benefit, as defined by national authority and/or ratified by national guidelines or equivalent, must have progressed following these therapies in order to be eligible for this study (*various solid tumors cohort, SCLC group only*)

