2. Patients who have had prior chemotherapy, targeted small molecule therapy, or radiation therapy within 2 weeks prior to study Day 1 or who have not recovered (i.e., \leq Grade 1 or at baseline) from adverse events due to a previously administered agent.

Note: Patients with \leq Grade 2 neuropathy or \leq Grade 2 alopecia are an exception to this criterion and may qualify for the study.

Note: If patients have received major surgery, they must have recovered adequately from the toxicity and/or complications from the intervention prior to starting therapy.

3. Patients who are currently participating and receiving study therapy or who have participated in a study of an investigational agent and received study therapy or who have used an investigational device within 4 weeks of the first dose of treatment.
4. Patients who have received prior therapy with an anti-PD-1, anti-PD-L1, anti-PD-L2, anti-CD137, or anti-Cytotoxic T-lymphocyte-associated antigen-4 (CTLA-4) antibody (including ipilimumab or any other antibody or drug specifically targeting T-cell co-stimulation or checkpoint pathways) or if the patient has previously participated in Merck MK-3475 clinical trials. (*Not applicable for various solid tumors cohort, head and neck squamous cell carcinoma, checkpoint inhibitor experienced group*)

5. Patients with known active central nervous system (CNS) metastases and/or carcinomatous meningitis.

Note: Patients with previously treated brain metastases may participate provided they are stable (without evidence of progression by imaging (using the identical imaging modality for each assessment, either MRI or CT scan) for at least four weeks prior to the first dose of trial treatment and any neurologic symptoms have returned to baseline), have no evidence of new or enlarging brain metastases, and are not using systemic steroids for at least 7 days prior to trial treatment. This exception does not include carcinomatous meningitis which is excluded regardless of clinical stability.

6. Patients with a known additional malignancy that is progressing or requires active treatment. Exceptions include basal cell carcinoma of the skin, squamous cell carcinoma of the skin that has undergone potentially curative therapy or in situ cervical cancer.
7. Patients who have a history of allergic reactions attributed to compounds of similar chemical or biologic composition to birinapant or pembrolizumab or their constituents.

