17. Patients who have disease that is suitable for local therapy administered with curative intent.
18. Patients who have received transfusion of blood products (including platelets or red blood cells) or administration of colony stimulating factors (including G-CSF, GM-CSF or recombinant erythropoietin)

within 4 weeks prior to study Day 1.

19. Patients who have a history or current evidence of any condition, therapy, or laboratory abnormality that might confound the results of the trial, interfere with the patient's participation for the full duration of the trial, or is not in the best interest of the patient to participate, in the opinion of the treating investigator.
20. Patients who have known psychiatric or substance abuse disorders that would interfere with cooperation with the requirements of the trial.
21. Patients who have severe hypersensitivity (\geq Grade 3) to pembrolizumab and/or any of its excipients.
22. Patient who have received anti-PD-L2, anti-CD137, or anti-cytotoxic T-lymphocyte-associated antigen-4 (CTLA-4) antibody (including ipilimumab or any other antibody or drug specifically targeting T-cell co-stimulation or checkpoint pathways) (*various solid tumors cohort, head and neck squamous cell carcinoma checkpoint inhibitor experienced group only*)
23. Patient who have previously received birinapant treatment

Study Drug Dose, Mode of Administration, and Administration Rate:

During a 21-day treatment cycle, patients will receive 200 mg pembrolizumab intravenously (IV) on Day 1 and IV birinapant on Days 1 and 8. A week without treatment (i.e., Days 15-21) will follow the second week of treatment, immediately after which the next 21-day treatment cycle will start. All doses will be administered via a 30-minute (+10 min) IV infusion. Pembrolizumab will be administered first on Day 1. The birinapant infusion will begin 30 minutes (+ 10 minutes) following the completion of the pembrolizumab infusion on Day 1. Patients will be eligible to receive study medication for 35 treatment cycles or until documentation of disease progression or unacceptable toxicity.

Study drug will be administered in the arm opposite to the site of blood-sample collection or via other venous access as appropriate.

Dose-escalation phase

Inter-patient dose escalation of birinapant will proceed at the birinapant dose indicated in the dose-escalation table, below. A minimum of 3 and up to 6 evaluable patients will be enrolled per dose level.

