Activation of non-canonical NF- κ B signaling by SMAC mimetics induces co-stimulatory activity in T cells and induces dendritic cell maturation leading to enhanced immune activation (Dougan et al. 2010, Muller-Sienerth et al. 2011, Knights et al. 2013). Proinflammatory cell death induction by SMAC mimetic also elicits the adaptive immune response, leading to increased Tumor Infiltrating Lymphocytes (TILs), interferon gamma production and activation of CD8 positive cytotoxic lymphocytes (Emeagi et al. 2012). The enhanced production of inflammatory cytokines in the local tumor microenvironment can be further enhanced by the combination of SMAC mimetics and anti-PD1 checkpoint inhibitors (Beug et al. 2017) which will then be expected to attract further immune cell infiltration to enhance the anti-tumor effect. These multiple mechanisms of enhanced immune activation lead to potent anti-tumor activity and synergistic combinations with multiple immunotherapy strategies (Dougan et al. 2010, Knights et al. 2013, Beug et al. 2015, Beug et al. 2017).

In particular, the combination of SMAC mimetics, including birinapant, with anti-PD1 checkpoint inhibitors leads to synergistic anti-tumor activity in preclinical models of glioblastoma, mammary tumors and multiple myeloma (Chesi et al. 2016, Beug et al. 2017). Birinapant was shown to enhance the TNF-dependent cytotoxic lymphocyte killing of tumor cells which was further enhanced by combination with anti-PD-1 antibodies (Kearney et al. 2017 Cell Death and Differentiation). These and other data provide a strong rationale for a potential benefit of combining birinapant with pembrolizumab due to two complementary

mechanisms:

- (1) Increased efficiency of activation of immune cells by activation of non-canonical NF- κ B signaling,
- (2) Increased local delivery of TNF α by activated T cells is converted to an induction of apoptosis as described above

These arguments support investigation of the combination of birinapant and pembrolizumab in various cancer indications and underpin the rationale for the selection of indications in the expansion phase of this study, which is further described in section 1.5.

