14. Patients who are pregnant or breastfeeding, or expecting to conceive or father children within the projected duration of the trial, starting with the screening visit

- through 120 days after the last dose of trial treatment. Pregnant women and men who want to conceive a child are excluded from this study because birinapant and pembrolizumab are agents with unknown potential for teratogenic or abortifacient effects in humans. Because there is an unknown risk for AEs in nursing infants secondary to treatment of the mother with birinapant and pembrolizumab, breastfeeding should be discontinued if the mother is treated on this study.
15. Patients who have a known history of Human Immunodeficiency Virus (HIV) (HIV 1/2 antibodies), or active Hepatitis B (e.g., HBsAg reactive). Patients with active Hepatitis C (e.g., HCV RNA [qualitative] is detected).
 16. Patients who have received a live-virus vaccination within 30 days of planned treatment start. Seasonal flu vaccines that do not contain live virus are permitted.
 17. Patients who have disease that is suitable for local therapy administered with curative intent.
 18. Patients who have received transfusion of blood products (including platelets or red blood cells) or administration of colony stimulating factors (including G-CSF, GM-CSF or recombinant erythropoietin) within 4 weeks prior to study Day 1.
 19. Patients who have a history or current evidence of any condition, therapy, or laboratory abnormality that might confound the results of the trial, interfere with the patient's participation for the full duration of the trial, or it is not in the best interest of the patient to participate, in the opinion of the treating investigator.
 20. Patients who have known psychiatric or substance abuse disorders that would interfere with cooperation with the requirements of the trial.
 21. Patients who have severe hypersensitivity (\geq Grade 3) to pembrolizumab and/or any of its excipients.
 22. Patients who have received anti-PD-L2, anti-CD137, or anti-Cytotoxic T-lymphocyte-associated antigen-4 (CTLA-4) antibody (including ipilimumab or any other antibody or drug specifically targeting T-cell co-stimulation or checkpoint pathways) (*Various solid tumor cohort, head and neck squamous cell carcinoma check point inhibitor experienced group only*)
 23. Patients who have previously received birinapant treatment.

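### Read literally, the catch-all in exclusion 22 conflicts with inclusion 19, which requires prior anti-PD-1/PD-L1 therapy in the checkpoint-inhibitor-experienced HNSCC group

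*Protocol*

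**What the plan says.** Four provisions of the protocol bear on prior checkpoint therapy in this group.

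- **Inclusion 19** (Synopsis, Section 4.1, Appendix 2.5.2). These patients "must have received prior therapy with an anti-PD-1 or anti-PD-L1 antibody, administered either as monotherapy, or in combination with other therapies". It also sets a minimum exposure: "Patients must have received at least two doses of an approved anti-PD-1/anti-PD-L1 antibody".
- **Exclusion 4** (Synopsis, Section 4.2). It bars five named classes (anti-PD-1, anti-PD-L1, anti-PD-L2, anti-CD137, anti-CTLA-4), ends the list with a catch-all, and separately bars earlier participation in MK-3475 trials. It carries a waiver: "Not applicable for various solid tumors cohort, head and neck squamous cell carcinoma, checkpoint inhibitor experienced group". Appendix 2.5.2, the group's own list, omits exclusion 4 altogether.
- **Exclusion 22** (Synopsis, Section 4.2, Appendix 2.5.2). In the Synopsis it reads "Patient who have received anti-PD-L2, anti-CD137, or anti-cytotoxic T-lymphocyte-associated antigen-4 (CTLA-4) antibody", followed in parentheses by "including ipilimumab or any other antibody or drug specifically targeting T-cell co-stimulation or checkpoint pathways". The Synopsis limits it to the "head and neck squamous cell carcinoma checkpoint inhibitor experienced group only".
- **How the criteria combine** (Sections 4.1 and 4.2). A patient must meet all inclusion criteria and is out on meeting any one exclusion.

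The SAP does not restate the criteria. Its Section 3 refers to the protocol for them.

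**The concern.** Exclusion 22 uses the same catch-all as exclusion 4. In exclusion 4 the phrase is harmless, because anti-PD-1 and anti-PD-L1 are barred there by name anyway. In exclusion 22 those two classes are off the named list, but "any other antibody or drug specifically targeting T-cell co-stimulation or checkpoint pathways" remains with nothing taken out of it. An anti-PD-1 or anti-PD-L1 antibody fits that description, and inclusion 19 demands one.

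What is at stake is consistent handling of eligibility. Under Section 6.2.1 enrolment needs confirmation by the sponsor or its CRO that the entry criteria are met. Section 4.3 treats a failure to meet them as a protocol violation and a ground on which the investigator may withdraw the patient. SAP Sections 4.1.2 and 5.5.2 have deviations classed as minor or major and listed. A site, a monitor and the CRO could each apply a different reading to the same patient.

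**Working it through.** No power, error-rate or sample-size figure is involved. The check is whether a patient can satisfy inclusion 19 and not meet exclusion 22.

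1. **What inclusion 19 requires.** At least two doses of an approved anti-PD-1 or anti-PD-L1 antibody. Every eligible patient in the group has this exposure.

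2. **What exclusion 22 bars by name.** Anti-PD-L2, anti-CD137 and anti-CTLA-4. Neither required class is named, so there is no conflict at this step.

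3. **What the catch-all adds.** It is defined by pathway rather than by class, and it reaches drugs as well as antibodies. The question is whether anti-PD-1/PD-L1 antibodies fall within checkpoint pathways as the protocol uses the term. They do. Section 1.1 says that combining SMAC mimetics "with anti-PD1 checkpoint inhibitors leads to synergistic anti-tumor activity" in preclinical models. Section 1.5.4.3 gives PD-1 alongside CTLA-4 as an example of an immune checkpoint. The group is itself called checkpoint-inhibitor experienced, and inclusion 19 defines that experience as prior anti-PD-1/PD-L1.

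4. **Whether an exception is stated.** The waiver on exclusion 4 is attached to exclusion 4 only. Exclusion 22 has no carve-out in the Synopsis, in Section 4.2 or in Appendix 2.5.2, and the SAP adds none.

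5. **Combining the steps.** By steps 1 and 3, anyone who meets inclusion 19 also falls under the literal catch-all. By step 4 nothing lifts it, and under Section 4.2 one exclusion is enough. On that reading alone, the set of eligible patients is empty.

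6. **Size.** The Synopsis plans 5 patients in this group.
   - Share of the various solid tumors cohort: 5/30 = 16.7%.
   - Share of the expansion phase: 28 + 27 + 26 + 30 = 111 patients, and 5/111 = 4.5%.

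7. **What depends on these patients.** The cohort's primary endpoint is descriptive safety and tolerability (Section 3.4.2.1), and Section 12.2 gives it no power calculation. SAP Section 5.6 confines formal testing to ORR in the colorectal, ovarian and cervical cohorts. The sensitivity analysis for wrongly included patients in SAP Section 5.6.5 repeats that primary efficacy analysis, so it does not reach this group. Under SAP Sections 5.2.1 and 5.2.3 an enrolled patient who has received both drugs stays in the ITT and safety populations whatever the eligibility finding.

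**The case against.** The strongest reply is that the criteria, read together, have a sensible meaning. The parenthesis in exclusion 22 opens as a gloss on the three classes before it, so it can be read as illustrating them and not as adding a further category. Exclusion 22 drops exactly the two classes that inclusion 19 requires. Exclusion 4 is waived for this group and absent from its own list. A reading that empties the group makes the waiver, the two deletions, inclusion 19 and the group's name pointless. Since the sponsor or its CRO confirms each enrolment, the party that created the group would presumably apply the intended meaning.

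Most of this stands. It shows what was intended, and it makes a complete failure to enrol unlikely. It does not supply the missing words. The catch-all extends to any other antibody or drug, which is wider than three antibody classes, and nothing limits it to them. Central confirmation makes a wrong refusal less likely, but it does not change the text against which a monitor or inspector would check the patient.

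Two stronger readings should be set aside. A reader might infer that exclusion 22 reinstates exclusion 4 in full. It does not: two named classes are gone, and so is the bar on earlier MK-3475 trial participation. A reader might also give the conflict weight because responses in patients who have progressed on anti-PD-1/PD-L1 are of special interest for judging what birinapant adds. That concerns attribution of efficacy in a five-patient group within a safety cohort. It has no bearing on whether the two criteria agree.

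**Conclusion.** Wrong as written: an internal inconsistency in the eligibility wording. Read literally, the catch-all in exclusion 22 bars the prior therapy that inclusion 19 requires. The intended exception can be inferred but is not stated anywhere in the protocol or SAP.

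It may be tempting to conclude that no patient can qualify for this group. The documents support that only for the literal reading. They also allow the narrower reading, and sites could enrol on evident intent. The supportable consequence is a risk that the 5 planned patients are refused, recorded as eligibility deviations, or handled differently between sites.

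The effect is confined to 5 of 30 patients in one descriptive safety cohort (5 of 111 in the expansion phase). The three Simon two-stage cohorts, their error rates and their decision rules are untouched. The conclusion rests on the protocol's own use of the word checkpoint and on its rule that any single exclusion disqualifies. It needs no outside source.

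**What to change.** Reconcile exclusion 22 with inclusion 19 in the Synopsis, Section 4.2 and Appendix 2.5.2. After the catch-all in each place, state that it does not cover the anti-PD-1 or anti-PD-L1 antibody that inclusion 19 requires. Inclusion 19 and the waiver on exclusion 4 can stay as they are. The bar on anti-PD-L2, anti-CD137, anti-CTLA-4 and other co-stimulation or checkpoint agents would remain, including where such an agent was given together with the required antibody.

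The cost is one phrase in three places, which can go into the next amendment. No patients, procedures or analyses are added, and the SAP needs no change.
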